## **2.0      Objectives**

### **2.1      Primary Objective**

To estimate the overall response rate (ORR) of the combination of standard dose azacitidine and ascorbic acid in patients with MDS, AML, and MDS/MPN overlap with *TET2* mutations.

### **2.2      Secondary Objective(s)**

To evaluate the following:

1. The safety profile of the combination of azacitidine and ascorbic acid in the targeted patient population.
2. The response duration for study patients.
3. The overall survival of the treated population (compared to matched historical cohort of patients treated with single agent Azacitidine)
4. The identification of genomic biomarkers that may predict response to the combination treatment.

5. Evaluation of changes in methylation prior and during therapy

### **3.0 Study Design**

This is an open-label, phase II study that will be conducted at Cleveland Clinic, Taussig Cancer Institute.

Azacitidine will be administered intravenously or subcutaneously at a fixed dose of 75mg/m^2/day for 7 consecutive days, (allowing for weekends, and holidays) of each 28-day cycle. Ascorbic acid will be administered orally daily at 1 g/day three days prior to start azacitidine and then continues daily for a total of 28 days of each 28 day cycle.

#### **3.1 Number of Subjects**

Approximately 28 patients will be enrolled in this trial.

#### **3.2 Expected Duration of Treatment and Subject Participation**

Upon signing consent, patients will be enrolled onto the study. Patients will undergo a screening period. The screening period is defined as the time period between the signing of the consent to the day the patient receives the first dose of study drug. During this period the patient will be assessed to determine if the patient meets all inclusion and exclusion criteria to be eligible for the study (Appendix IV).

The treatment period is defined as the time between first day of study drug dosage (Day - 3) to C6D28. At this time the patient will be assessed and eligible to move into the Extended Treatment Period (ETP). The extended treatment period is defined as C7D1 to the patient meets EOT criteria (Section 6: Table 1; Appendix IV)

Study treatment is defined as the treatment period and if applicable the extended treatment period (Appendix IV). Study drug will be continued during the duration of the study treatment unless patients exhibit any EOT criteria (Section 6: Table 1; Appendix IV).

Treatment should be continued for at least 6 cycles in the absence of toxicities that require discontinuation and/or any EOT criteria (Section 6: Table 1; Appendix IV). After 6 cycles of treatment, a bone marrow biopsy and aspiration will be obtained to evaluate response. If patient has achieved either of the below response criteria (Appendix IV) based on their disease diagnosis patient will be eligible continue onto the extended treatment period (ETP). The patient is eligible to remain on treatment during the ETP until disease progression or patient meets EOT criteria (Section 6: Table 1; Appendix IV).

#### Response Criteria for extended treatment eligibility

- complete remission, partial remission, or hematologic improvement (CR/PR/HI) per IWG 2006 criteria for patients with MDS
- (CR/PR/marrow CR) per IWG 2003 criteria for patients with AML
- If the response is stable disease and the investigator determines the patient is gaining clinical benefit, patient may continue on treatment until progression.

At the point in which the patient meets the any EOT criteria (Section 6) the patient will enter into the follow up period to follow for survival status. The patient will be followed for up to 1 year and/or death, whichever were to occur first. End of study (EOS) is defined as the time the patient completes 1 year of survival follow up and/or patient's death, whichever were to occur first.

#### **4.1 Subject Selection**

#### **4.2 Inclusion Criteria**

Subjects must meet all of the following inclusion criteria to be eligible for enrollment:

4.2.1 Patients must have a confirmed *TET2* mutations identified by next generation targeted deep sequencing.

4.2.2 Patients must have MDS, or MDS/MPN overlap defined by 2016 WHO criteria. Both newly diagnosed or previously treated MDS or MDS/MPN patients are eligible as long as the patient has never received prior treatment with azacitidine or decitabine.

4.2.3 Patients with Leukemic/blast phase transformation MPN.

4.2.4 Patient with AML according to 2016 WHO criteria (excluding APL [AML-M3]).

4.2.4.1 Newly diagnosed patients who are ineligible or declined to receive intensive chemotherapy after discussion of risks and benefits of that approach or patients with primary refractory/relapsed AML.

4.2.4.2 Patients with active central nervous system (CNS) leukemia eligible at the discretion of treating physician.

4.2.4.3 Relapse/Refractory is defined as at least 1 course of treatment for AML excluding any patients treated with azacitidine or decitabine.

4.2.4.3.1 Patients should be off any prior treatment or line of therapy for 2 weeks prior to start study with the exception of hydrea (Hydroxyurea).

4.2.5 Prior therapy with hydroxyurea, biological or targeted therapy (e.g. flt3 inhibitors, other kinase inhibitors) or hematopoietic growth factors is allowed.

4.2.6 Age  $\geq 18$  years.

4.2.7 ECOG performance status  $\leq 3$ .

4.2.8 Patients must have normal organ and marrow function as defined at the discretion of the treating physician and PI.

- 4.2.9 Women of childbearing potential must have a negative serum or urine pregnancy test within 10-14 days prior to enrollment.
- 4.2.10 Patients must have the ability to understand and the willingness to sign a written informed consent document.
- 4.2.11 Patient must be willing to comply with all aspects of the protocol including completing the drug diary.
- 4.2.12 Patient must discontinue any and all use of multivitamin and/or vitamin c medication 24 hours before first dose of Ascorbic Acid.

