## 1.2 Name and Description of Azacitidine

Azacitidine, a ring analog of the pyrimidine nucleoside cytidine, has effects on cell differentiation, gene expression, and DNA synthesis and metabolism. Since the early 1970s, azacitidine has been investigated in the US for the treatment of acute leukemia. Clinical trials have focused primarily on patients with disease refractory to conventional chemotherapy. These investigations indicated azacitidine has activity in the treatment of acute myeloid leukemia (AML). Clinical trials subsequently have been conducted to evaluate the effects of azacitidine in a variety of other malignant and hematologic disorders, including solid tumors, hemoglobinopathies (thalassemia and sickle cell anemia), and myelodysplastic syndromes (MDS).

Toxicology studies have been conducted in mice, rats, dogs, and Rhesus monkeys. Most

of the studies were performed during the 1970s and early 1980s according to existing guidelines and standards in place during that period. The nonclinical studies identified the bone marrow, liver, kidneys, and lymphoid tissues (spleen, lymph nodes) as the main target organs of toxicity. In single-dose studies, the lethal dose of azacitidine after intravenous (IV) administration in mice, rats, and dogs was approximately  $250 \text{ mg/m}^2$ . Repeated daily dosing appears to increase the toxicity of azacitidine. The genotoxicity of azacitidine is consistent with that of other nucleoside analogs that interact with nucleic acids. Likewise, similar to other agents with cytostatic properties, azacitidine was embryotoxic and reduced the reproductive performance in mice and rats. It is important to note that animal study data is superseded in many respects by the extensive clinical safety data collected in the last two decades.

Limited azacitidine pharmacokinetic data are currently available. Based on plasma concentrations of total radioactivity (which represent parent drug plus circulating metabolites), azacitidine is rapidly absorbed when given subcutaneously (SC), with maximum plasma concentrations found 0.5 to 2 hours after dosing. Azacitidine and/or its by-products are rapidly cleared by the kidneys. The half-lives and percent radioactivity recovered in urine are similar for the IV and SC routes of administration.

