## **4.2 Exclusion Criteria**

The presence of any of the following will exclude a subject from study enrollment:

- 4.2.1 Any prior treatment with azacitidine or decitabine.
- 4.2.2 Patients diagnosed with APL, AML-M3.
- 4.2.3 Patients receiving other active treatment for their myeloid malignancy including investigational agents with the exception of hydrea for WBC control.
- 4.2.4 Nursing or pregnant women.
- 4.2.5 History of allergic reactions to either azacitidine or ascorbic acid.
- 4.2.6 Patients with uncontrolled intercurrent illness including, but not limited to ongoing or active infection, symptomatic congestive heart failure, unstable angina pectoris, cardiac arrhythmia, or psychiatric illness/social situations that would limit compliance with study requirements.

4.2.7 Patients with higher risk of bleeding (deemed by the treating physician) or on anticoagulation.

4.2.8 Patients who are unwilling or unable to comply with all study requirements.

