#### **6.4 Criteria for Removal from Study Treatment (EOT)**

In the absence of treatment delays due to adverse events, treatment may continue for 6 cycles or be extended after 6 cycles unless 1 one of the following criteria applies:

End of Treatment Criteria

• Disease progression defined as no response after 6 months of treatment or loss of response during treatment as defined in section 12

• Intercurrent illness that prevents further administration of treatment

• The investigator and/or treating physician considers it to be in the best interest of the subject to permanently discontinue study treatment

○ This includes if the treatment is deemed to be of excessive toxicity to the patient by the treating physician

• Patient decision to withdraw from treatment (partial consent) or from the study (full consent)

• Pregnancy during the course of the study for a child-bearing participant

• Death

• Unacceptable adverse events defined as following:

○ Unacceptable treatment related toxicity, NCI CTC AE version 4.0 Grade 3 or 4 that fails to recover to baseline or < Grade 3 in the absence of treatment within 4 weeks

○ Any toxicity or other issue that causes a delay of study drug administration by more than 4 weeks

Table 1: End of Treatment Criteria

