#### **Treatment Period (Day -3 to C6D28)**

1. Hematology exams (Appendix VI) at the start of each cycle (day 1) and the last day of cycle 6 (C6D28)
2. Serum Chemistry (Appendix VI), including Creatinine, bilirubin, ALT or AST at the start of each cycle (day 1)
3. Bone marrow aspirate and/or biopsy to confirm response, to be performed at the end of cycle 6. 10 ML of whole blood or bone marrow aspirate whichever available will be collected in extra lab tube. All bone marrows samples are to be stored at Cleveland Clinic
4. Conventional cytogenetics to be performed at the end of cycle 6
5. Documentation of frequency of transfusions (only PRBC and Platelets) prior to start of each new cycle.
6. Documentation in the medical record of any grade 2 or higher adverse events at each visit. For guidelines on SAE Reporting and AE entry for Case Report
7. Documentation of any prior administration of growth factors and ESA prior to start of each cycle
8. A 10 ML blood sample that will be used for next generation targeted deep sequencing of genes that are common in myeloid malignancies

9. Physical exam and ECOG performance status occurring at the end of each cycle
10. Vital signs occulting at each visit
11. Pregnancy test if applicable
12. MDS Response Assessment, assessed by the treating physician occurring at the end of cycle 6 or EOT, whichever occurs first.
13. Methylation panel only occurring in Cycle 1
14. Azacitidine will be administered intravenously or subcutaneously at a fixed dose of 75mg/m^2/day for 7 consecutive days, (allowing interruptions for weekends, and holidays, of each 28-day cycle).
15. Ascorbic acid will be administered orally daily at 1 g/day three days prior to start azacitidine and then continues daily for a total of 28 days of each 28 days cycle.

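### Azacitidine is described as embryotoxic, yet the entry criteria set no contraception condition, on-treatment pregnancy testing has no stated timing in Section 11.1, and the extended-treatment list has no pregnancy test

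*Combined protocol and SAP*

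**What the plan says.** All references are to the combined protocol and SAP.

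- **Hazard.** Section 1.2, on animal toxicology: "azacitidine was embryotoxic and reduced the reproductive performance in mice and rats".
- **Entry.** Inclusion item 4.2.9: "Women of childbearing potential must have a negative serum or urine pregnancy test within 10-14 days prior to enrollment". Exclusion item 4.2.4: "Nursing or pregnant women". Neither list mentions contraception, for women or for men.
- **Stopping.** Section 6.4, Table 1, lists as an end-of-treatment criterion: "Pregnancy during the course of the study for a child-bearing participant".
- **Cycles 1 to 6.** Section 11.1, Treatment Period, item 11, reads in full: "Pregnancy test if applicable".
- **Cycles 7 and later.** The Extended Treatment Period list in Section 11.1 has hematology and chemistry on Day 1 of each cycle (items 5 and 6) and continued azacitidine (item 7). It has no pregnancy test. Sections 3.2 and 6.2 let this period run until an end-of-treatment criterion is met, with no maximum.
- **Calendar (Section 11.2).** The pregnancy-test row carries a mark at screening and one later mark.

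**The concern.** The protocol treats pregnancy as incompatible with treatment both at entry and afterwards, but the written lists do little to prevent it or to detect it early. A rule that stops treatment on pregnancy works only once the pregnancy is known.

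A site that performs only the tests with a scheduled time could give several azacitidine courses between the entry test and the next one. In extended treatment it could continue with no listed test at all. An unsuspected early pregnancy could then be exposed repeatedly before Table 1 takes effect. Conception by the partner of a male participant is not addressed in the text available.

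This is a question of patient safety. It has no bearing on the response endpoint, the two-stage design or its error rates.

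**Working it through.** The plan gives no figure to reproduce here, so the check sets the sections side by side and then counts doses to show scale.

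**1. Timing in the Section 11.1 list.** Item 11 gives no day or interval. Some neighbouring items do: item 12 reads "MDS Response Assessment, assessed by the treating physician occurring at the end of cycle 6 or EOT, whichever occurs first" and item 13 reads "Methylation panel only occurring in Cycle 1". Item 8, the sequencing blood draw, also gives none, so a missing time in the list is not decisive by itself. The calendar has to be read with it.

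**2. The calendar mark.** Counting cells with the row label as column 0:

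| Row | Columns with a mark |
|---|---|
| Pregnancy test | 1, 15 |
| Bone marrow | 1, 15 (footnote h), 18 (footnote i) |
| Disease response assessment | 1, 15, 16, 18 |
| Ascorbic acid dispensing | 2, 6, 8, 10, 12, 15 |

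The Cycle 6 header starts at column 14 and the extended-treatment header is column 16. Column 15 is shared with the marrow, which Section 11.1 item 3 times as "Bone marrow aspirate and/or biopsy to confirm response, to be performed at the end of cycle 6", and footnote H ties that mark to cycle 6. The likeliest reading of the later pregnancy-test mark is therefore cycle 6. Ascorbic acid dispensing also has a mark there, so C6D1 is possible as well as C6D28.

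The table is damaged in the text available. The azacitidine and Day rows stop at column 10, and the optional end-of-treatment marrow (footnote I) sits under Follow up. An empty cell therefore does not prove that no test was planned.

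**3. Illustrative gap before the cycle 6 test.** Assumptions: 28-day cycles without delay, 7 azacitidine doses per cycle, the cycle 6 reading, and item 11 not used earlier. Counting from C1D1:

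- Test at C6D1, before that day's dose: 5 × 28 = 140 days, after 5 × 7 = 35 doses.
- Test at C6D28: 5 × 28 + 27 = 167 days, after 6 × 7 = 42 doses.

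Section 7.0 allows up to 4 weeks' prolongation between cycles after the first two courses. Four such intervals precede cycle 6, so at most 4 × 28 = 112 days are added, giving 252 to 279 days. The dose counts do not change.

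**4. Illustrative extended treatment.** There is no stated maximum, so the end points below are assumed. Doses given after the cycle 6 test with no further test listed:

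| Treatment ends after | Test at C6D28 | Test at C6D1 |
|---|---|---|
| Cycle 9 | 3 × 7 = 21 | 4 × 7 = 28 |
| Cycle 12 | 6 × 7 = 42 | 7 × 7 = 49 |

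Footnote G lets the C6D28 visit serve as C7D1 when there is no dosing delay. A C6D28 test can then cover entry to cycle 7, but nothing is listed after it.

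**5. Comparison.** A test before azacitidine on Day 1 of each cycle leaves at most 7 doses between consecutive tests.

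**The case against.** The strongest reply is that much of the apparent gap may not be a gap in the plan.

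- **Consent form.** Its pages are not in the text available and may require contraception. This stands. A reader might infer that the trial has no contraception requirement at all; the documents support only the narrower statement that the entry criteria contain none. Contraception wording in a consent form would not, however, set a testing schedule.
- **Calendar.** A reader might infer that no test is planned on treatment. That does not hold: item 11 lists one, and the calendar shows a mark after screening. Given the state of the table, further marks may have been lost. The absence of a test from the extended-treatment list does not depend on the calendar.
- **Clinical judgement.** Item 11 permits testing at any time, patients are examined every cycle, and never testing a woman to whom the item applies is arguably not compliant. This is fair, but the item permits without requiring any particular time, and no equivalent item exists for cycles 7 and later.
- **Population.** Section 1.1 gives a median age of about 70 for MDS, which points to few women of childbearing potential. This stands for the size of the issue. But entry is from age 18, AML is included, men are enrolled, and the protocol itself provides for such participants in item 4.2.9 and Table 1.

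**Conclusion.** The point holds as a low-cost patient-safety improvement. Three facts rest on the text alone: the entry criteria set no contraception condition, item 11 gives no timing, and the open-ended extended-treatment list has no pregnancy test although Day 1 blood is drawn every cycle. The calendar probably adds a single test in cycle 6.

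The 140 to 167 days, the 35 to 42 doses and the extended-treatment counts only illustrate scale. They depend on a damaged table, on item 11 not being used earlier, and on assumed treatment lengths. They should not be read as the exposure that any participant will have, or as a pregnancy risk, which the documents give no basis to quantify. The number of participants affected is not stated and is likely to be few, possibly none. The endpoint, sample size and error rates are unchanged.

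**What to change.** 1. After inclusion item 4.2.9, add that women of childbearing potential, and men with partners of childbearing potential, agree to use effective contraception during treatment and for a sponsor-defined period afterwards. If the consent form already has such wording, use it.
2. Replace item 11 of the Treatment Period list in Section 11.1 with a urine or serum pregnancy test before azacitidine on Day 1 of each cycle for women of childbearing potential.
3. Add the same item to the extended-treatment list for cycles 7 and later. Let a C6D28 test count for C7D1 where footnote G applies.
4. Align the pregnancy-test row of the calendar.

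The cost is a short amendment and a few inexpensive tests at visits where blood is already drawn (items 1 and 2 of the Treatment Period list, items 5 and 6 of the extended-treatment list). Only the few women concerned are tested. The contraception condition could deter an occasional eligible patient.

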### **1.3 Name and Description of Ascorbic Acid**

Ascorbic acid is a water-soluble vitamin. Ascorbic acid has few strictly pharmacological actions. Administration in amounts greatly in excess of physiologic requirements causes no demonstrable effects. The vitamin is an essential coenzyme for collagen formation, tissue repair and synthesis of lipids and proteins. It acts both as a reducing agent and as an antioxidant and is necessary for many physiologic functions, e.g., metabolism of iron and folic acid, resistance to infection, and preservation of blood vessel integrity. Signs and symptoms of early AA deficiency include malaise, irritability, and arthralgia, hyperkeratosis of hair follicles, nosebleed, and petechial hemorrhages. Prolonged deficiency leads to clinical scurvy.

Ascorbic acid is normally present in both plasma and cells. The absorbed vitamin is ubiquitous in all body tissues. The highest concentrations are found in glandular tissue, the lowest in muscle and stored fat. Ascorbic acid is partially destroyed and partially excreted by the body. There is a renal threshold for AA; the vitamin is excreted by the kidney in large amounts

only when the plasma concentration exceeds this threshold, which is approximately 1.4 mg/100 mL. When the body is saturated with ascorbic acid, the plasma concentration will be about the same as that of the renal threshold; if further amounts are then administered, most of it escapes into the urine. When body tissues are not saturated and plasma concentration is low, administration of ascorbic acid results in little or no renal excretion.

A major route of metabolism of ascorbic acid involves its conversion to urinary oxalate, presumably through intermediate formation of its oxidized product, dehydro-ascorbic acid. In a study of healthy volunteers at the NIH, an in-hospital depletion-repletion study was conducted. Seven healthy volunteers were hospitalized for 4-6 months and consumed a diet containing <5 mg of AA daily. Steady-state plasma and tissue concentrations were determined at seven daily doses of vitamin C from 30 to 2500 mg. AA steady-state plasma concentrations as a function of dose displayed sigmoid kinetics. Complete plasma saturation with AA occurred at 1000 mg PO daily.

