## **10.0 EXPLORATORY or CORRELATIVE STUDIES**

A blood sample will be obtained for a next generation targeted deep sequencing genomic panel of 170 gene mutations prior to start treatment. Quantification of 5hmC and 5mC in patient's derived mononuclear cells will be obtained during the screening period and on C6D15 to evaluate for changes in methylation. We will use the ELISA, dot-blot and mass spec assay to measure the level of 5hmC, a signature for TET2 activity in HSPCs and 5mC an indicator of the lack of TET2 activity in patient derived PBMCs (Peripheral blood mononuclear cells) and bone marrow cells. For this purpose total genomic DNA from whole cell nuclear lysates (PBMCs or Bone marrow) or from the nuclear lysate of CD34+ cells will be extracted and used for ELISA assay using a known standard curve. The mass spec will be performed on the samples after digesting with NaOH (Ref: Nature 468, 839–843) and separated and quantified by LCMS-MS (Ref: Mo Cell; Volume 64, Issue 5, 1 December 2016, Pages 913–925) utilizing X-bridge reverse phase column. Recombinant TET2 protein will be used to prepare the standard reaction mixture for 5hmC determination and comparison to the patient samples.

All samples obtained will be shipped to and stored at The Cleveland Clinic. Samples will remain at the Cleveland Clinic to be used for research purposes for this study as well as for future research projects approved by the IRB.

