## 11.2 Calendar

Period	Screening Period (Day-17 to Day -3)	Treatment Period														Extended Treatment Period Cycles	End Of Treatment (EOT)	Follow up k
		Cycle 1				Cycle 2		Cycle 3		Cycle 4		Cycle 5		Cycle 6				
Day		-3	1	7 c	14 n	1	7 c	28 g	1	7 c								
Administration of Azacitidine			X	X b		X	X b		X	X b								
Ascorbic Acid Dispensement		X a				X		X		X		X			X			
disease history and prior therapies	X																	
Record RBC/ platelets transfusion	X	X				X		X		X		X		X	X	X		
History and physical exam dm	X	X				X		X		X		X		X	X			X j
Vital signs d	X	X	X	X		X	X	X	X	X	X	X	X	X	X	X		X j
ECOG performance status em	X	X				X		X		X		X		X	X			X
Hematology dm	X	X				X	X	X	X	X	X	X	X	X	X	X		X j
Serum Chemistry d m	X	X				X		X		X		X		X	X			X
Pregnancy test	X														X			
Disease response assessment f	X														X	X		X
Bone marrow biopsy and aspiration L	X														X h			X i
Mutational analysis blood draw L	X l														X			
Methylation profile blood draw L	X		X	X	X													
Drug Diary Accountability		X				X		X		X		X		X	X	X		
Survival Follow up																		X k
Record adverse events m			↔ X →															

- A: For Cycle 1 only, patient will begin treatment with Ascorbic Acid 3 days prior to initial treatment of Azacitidine
- B: Azacitidine administration has a +/- 3 day window to account for breaks in treatment for weekends, and holidays
- C: Day 7 has a +/- 3 day window to account for breaks in treatment for weekends, holidays, and institutional standards
- D: See Appendix VI for required tests
- E: See Appendix I for performance status grading
- F: See Section for 12.0 for MDS/AML response assessment criteria
- G: If patient is eligible for the extended treatment period, and moving forward on the next cycle without a dosing delay, the C6D28 visit can serve as the visit of C7D1. If the patient is not eligible for the extended treatment period the patient's C6D28 visit can serve as the EOT visit.
- H: The cycle 6 bone marrow biopsy can occur up to 14 days (C6D14) prior to the C6D28 visit.
- I: EOT bone marrow biopsy is optional per discretion of the treating physician

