- J: These tests in follow up are optional pending discretion of the treating physician
- K: Survival Follow Up will occur bimonthly (60 days +/- 7 days) for a duration of 1 year from patient's EOT visit.
- L: 10 mL of whole blood or bone marrow aspirate whichever available will be collected in extra lab tube for these tests.
- M: If these procedures require a physician visit, these can occur 3 calendar days prior to the day 1 of that cycle (window of - 3 days).
- N: Cycle 1 Day 14 has a +/- 1 day window to account if the day falls on a holiday or weekend.

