#### **APPENDIX IV: STUDY DESIGN TIME POINT DEFINITIONS**

Study Time Points	Definitions
Screening	Screening will occur from the time of the consent until day -4
Baseline/Enrollment	Days -17 b to Day -3 c
Treatment Period	Day 1 c to C6D28 or patient meets end of treatment criteria before completing 6 cycles
Extended Treatment Period (ETP)	The extended treatment period is defined as C7D1 to the patient meets EOT criteria
Study Treatment	The treatment period and if applicable the extended treatment period
End of Treatment (EOT)	The day patient meets the defined EOT criteria (Table 1) and discontinues study treatment.
Follow up	Patient will be followed bimonthly (60 days +/- 7 days) for a duration of 1 year after study
End of Study (EOS)	The time the patient completes 1 year of survival follow up and/or patient's death, whichever were to occur first.

A: Day 1 is defined as first dose of Azacitidine  
B: Day -17 is defined as 14 days prior to first dose of study Drug (Day -3)  
C: Day -3 is defined as day of Study Drug

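### The baseline methylation sample may be drawn while a patient still takes vitamin C, and from marrow when later samples are blood, so the within-patient change can be distorted

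*Combined protocol and SAP*

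**What the plan says.** Section 2.2, item 5, sets the objective: "Evaluation of changes in methylation prior and during therapy".

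**Timing of the samples.** Section 10.0 says that the 5hmC and 5mC measurements "will be obtained during the screening period and on C6D15 to evaluate for changes in methylation". The calendar in section 11.2 heads its first column "Screening Period (Day-17 to Day -3"). Appendix IV differs slightly: "Screening will occur from the time of the consent until day -4". For on-treatment samples, section 11.1 (Treatment Period, item 13) confines the methylation panel to Cycle 1. The calendar row reads as Cycle 1 Days 1, 7 and 14.

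**Vitamin C.** Inclusion criterion 4.2.12 reads: "Patient must discontinue any and all use of multivitamin and/or vitamin c medication 24 hours before first dose of Ascorbic Acid". Calendar footnote A fixes the first study dose: "For Cycle 1 only, patient will begin treatment with Ascorbic Acid 3 days prior to initial treatment of Azacitidine". Section 11.1 (screening items 7 and 8) requires supplement use and the stop date to be recorded.

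**Tissue.** Calendar footnote L, attached to the methylation row among others, reads: "10 mL of whole blood or bone marrow aspirate whichever available will be collected in extra lab tube for these tests". Section 10.0 mentions DNA from blood mononuclear cells, marrow and CD34+ cells.

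**Analysis.** Section 14.0 describes no methylation analysis and no adjustment for tissue or earlier vitamin C.

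**The concern.** The trial has one arm, so evidence on whether ascorbic acid changes methylation comes from comparing each patient with his or her own baseline. That needs a baseline free of the agent under study and taken from the same kind of cells as the later samples. The plan secures neither.

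The protocol's own background shows why earlier vitamin C matters. Section 1.1 states that it enhances basal TET activity, and section 1.3 reports: "Complete plasma saturation with AA occurred at 1000 mg PO daily". That is the study dose, and a patient could be taking as much over the counter when the baseline tube is drawn. No later sample can stand in, because the first on-treatment draw in the calendar, Cycle 1 Day 1, follows three days of study ascorbic acid.

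At stake are objective 5 and the correlative aim of relating methylation to response. A small change could mean no effect, or a baseline already raised. A large one could mean an effect, or a comparison of marrow with blood.

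**Working it through.** The documents give no effect size, standard deviation, power or test for the methylation change, so there is no figure of the plan to reproduce.

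**1. Sampling window against the stop rule (from the documents)**
- Permitted baseline days in the calendar: Day -17 to Day -3, which is 15 days.
- First study tablet on Day -3, so the latest stop, 24 hours earlier, is Day -4.
- Permitted days before Day -4: Day -17 to Day -5, which is 13 of 15.
- Under Appendix IV, screening starts at consent and ends on Day -4, so Day -3 is not available.

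This counts opportunities. It does not measure bias.

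**2. Is supplement exposure relevant? (from the documents)**
- Section 1.3 puts saturated plasma at about the renal threshold, 1.4 mg/100 mL, and elsewhere equates 350 mg/dL with 20 mM.
- So 1.4 / 350 × 20 mM = 0.08 mM, or 80 µM.
- The cell-line experiment in section 1.1 used 100 µM for 12 hours.

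A saturated supplement user is thus near the concentration at which the sponsor tested for an effect. Plasma and cell culture are not the same setting, so this shows plausibility only.

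**3. Tissue available at each time point (from the documents)**
- Screening: marrow biopsy scheduled, so blood or marrow.
- Cycle 1 Days 1, 7 and 14: no marrow scheduled, so blood.
- C6D15 (section 10.0 only): the cycle 6 marrow may be taken from C6D14 (footnote H), so blood or marrow.

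On the Cycle 1 schedule, a marrow baseline followed by blood is an ordinary result of the plan. On the section 10.0 schedule, same-tissue pairs are feasible but not required.

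**4. Sensitivity to earlier vitamin C (assumed inputs)**

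Let f be the share of prior users and s the share of the effect already present at their baseline. The fraction of the mean change retained is k = 1 − f × s. For s from 25% to 100%:
- f = 10%: k = 90% to 97.5%
- f = 25%: k = 75% to 94%
- f = 50%: k = 50% to 87.5%

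For an assumed true paired change of 0.5 SD, 28 pairs and two-sided 0.05, power ≈ Φ(0.5 × k × √28 − 1.96):
- k = 1: 75%
- k = 0.875: 64%
- k = 0.75: 51%
- k = 0.50: 26%

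**5. Sensitivity to a tissue switch (assumed inputs)**

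Let g be the share of patients who switch, all in the same direction, and T the tissue difference in SDs of the paired change. The false mean change is g × T. With z = gT√28 / √(1 + g(1 − g)T²), a paired test with no drug effect rejects with probability Φ(z − 1.96) + Φ(−z − 1.96). For T from 0.5 to 1:
- g = 10%: false change 0.05 to 0.10 SD; rejects in 6% to 8%
- g = 25%: 0.125 to 0.25 SD; 10% to 23%
- g = 50%: 0.25 to 0.50 SD; 25% to 66%

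The documents give none of f, s, g or T.

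**The case against.** **The early draw is allowed, not required.** This stands. A sample on Day -3 before the first tablet complies with the calendar, and 4.2.12 sets only the latest stop. A reader might infer that baselines are taken on vitamin C as a rule; the text supports only that they may be.

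**A Day -3 draw would not guarantee a clean baseline.** This also stands. A patient who stops on Day -4 is only 24 hours off supplements, and nothing in the documents says how fast plasma ascorbate or 5hmC falls back. The later draw shortens the possible overlap, and the split by prior use deals with what remains.

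**The tissue problem depends on the schedule.** This stands in part. If C6D15 is the on-treatment sample, marrow can be had at both ends. But section 11.1 and the calendar place the draws in Cycle 1, where no marrow is scheduled, and neither schedule requires matching tissue.

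**Other text points to blood, and a tissue rule may exist elsewhere.** The calendar row is labelled a blood draw, section 10.0 names mononuclear cells and can be read as measuring both blood and marrow, and footnote L is shared with other rows. The contents also list a section 10.1 on sample collection that is not in the text available here. It cannot be said, therefore, that the plan has no matching rule anywhere. Footnote L is nonetheless attached to the methylation row and expressly leaves the choice to availability.

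**This is a correlative readout without a planned test.** True, and it limits the weight of the point without removing the ambiguity.

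**Conclusion.** The concern holds as a weakness in how the methylation change is measured. The plan permits a baseline taken during the patient's own vitamin C use, and permits the tissue to differ between baseline and follow-up. Earlier vitamin C would mainly shrink the apparent change in 5hmC; a tissue switch could bias it in either direction.

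The only sizes that come from the documents are the window count (13 of 15 permitted days precede the latest stop day) and the exposure comparison. The attenuation, power and false-positive figures are illustrations on assumed inputs, ranging from negligible (2.5% of the change lost) to serious (half lost, or a false signal in most trials).

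A reader might conclude that the methylation results will be uninterpretable. The documents do not support that, because they give neither the frequency of prior use nor the tissue difference. Nor does the point touch the primary analysis: the response endpoint and its decision rule do not use these samples. It is a cheap improvement worth making, because a baseline cannot be recovered once dosing has begun.

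**What to change.** 1. **One tissue.** For the change analysis, replace the availability rule in footnote L with peripheral blood mononuclear cells at every time point, as the calendar row already implies. Report marrow and CD34+ results separately, as same-tissue pairs only.
2. **Baseline on Day -3.** Draw the baseline methylation tube at the existing Day -3 visit, before the first ascorbic acid tablet, and align section 10.0 and Appendix IV. State that this guarantees only 24 hours off supplements.
3. **Split by prior use.** Report the change separately for recent vitamin C users and non-users, from the stop dates already recorded under section 11.1. Define recent use before the samples are assayed.
4. **Reconcile the time points.** Section 10.0 (C6D15) and section 11.1 with the calendar (Cycle 1 only) must agree before the phrase during therapy has a fixed meaning.

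**Cost.** One tube moves to a visit at which ascorbic acid is already dispensed, and a few sentences change. No visit, procedure or patient is added. Patients with only a marrow baseline drop out of the paired blood analysis, and with about 28 patients the user and non-user groups will be small, so that split can only be descriptive.
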